no	XL_HDL_C	0.068	0.062	t-test	0.918	-0.123	0.731	0.262
no	XL_HDL_CE	0.049	0.044	t-test	0.909	-0.138	0.636	0.224
no	XL_HDL_FC	0.019	0.018	t-test	0.943	-0.085	0.756	0.264
no	XL_HDL_FC_pct	15.933	17.975	t-test	1.128	0.174	0.844	0.308
no	XL_HDL_L	0.141	0.123	t-test	0.875	-0.193	0.897	0.331
no	XL_HDL_P	0	0	t-test	0.913	-0.132	0.662	0.227
no	XL_HDL_PL	0.06	0.049	t-test	0.814	-0.297	1.022	0.384
no	XL_HDL_PL_pct	37.258	33.048	t-test	0.887	-0.173	1.267	0.407
no	XL_HDL_TG	0.012	0.012	t-test	0.933	-0.1	0.376	0.158
no	XL_HDL_TG_pct	10.56	10.531	t-test	0.997	-0.004	0.015	0.004
no	XL_VLDL_C	0.089	0.081	t-test	0.918	-0.124	0.471	0.183
no	XL_VLDL_CE	0.047	0.046	t-test	0.966	-0.05	0.149	0.054
no	XL_VLDL_CE_pct	14.714	17.751	t-test	1.206	0.271	1.142	0.407
no	XL_VLDL_C_pct	25.817	29.087	t-test	1.127	0.172	1.084	0.385
no	XL_VLDL_FC	0.041	0.036	t-test	0.863	-0.213	0.988	0.368
no	XL_VLDL_FC_pct	11.103	11.336	t-test	1.021	0.03	0.48	0.183
no	XL_VLDL_P	0	0	t-test	0.857	-0.222	1.223	0.407
no	XL_VLDL_PL	0.071	0.061	t-test	0.851	-0.232	1.151	0.407
no	XL_VLDL_PL_pct	18.5	18.311	t-test	0.99	-0.015	0.376	0.158
no	XL_VLDL_TG_pct	55.683	52.602	t-test	0.945	-0.082	1.051	0.384
no	XS_VLDL_C	0.183	0.184	t-test	1.01	0.014	0.074	0.024
no	XS_VLDL_CE	0.12	0.122	t-test	1.015	0.021	0.137	0.049
no	XS_VLDL_CE_pct	29.837	31.525	t-test	1.057	0.079	1.028	0.384
no	XS_VLDL_C_pct	44.926	46.821	t-test	1.042	0.06	1.089	0.385
no	XS_VLDL_FC	0.062	0.062	t-test	1	0.001	0.003	0.003
no	XS_VLDL_FC_pct	15.089	15.296	t-test	1.014	0.02	0.738	0.264
no	XS_VLDL_L	0.417	0.414	t-test	0.992	-0.011	0.045	0.009
no	XS_VLDL_P	0	0	t-test	0.997	-0.005	0.021	0.004
no	XS_VLDL_PL	0.124	0.122	t-test	0.985	-0.021	0.078	0.026
no	XS_VLDL_PL_pct	29.481	28.941	t-test	0.982	-0.027	0.738	0.264
no	XS_VLDL_TG	0.111	0.107	t-test	0.971	-0.042	0.157	0.057
no	XS_VLDL_TG_pct	25.593	24.238	t-test	0.947	-0.078	0.909	0.337
no	XXL_VLDL_C	0.118	0.104	t-test	0.885	-0.177	0.589	0.219
no	XXL_VLDL_CE	0.067	0.061	t-test	0.913	-0.131	0.372	0.158
no	XXL_VLDL_CE_pct	17.383	18.837	t-test	1.084	0.116	0.223	0.088
no	XXL_VLDL_C_pct	28.919	30.122	t-test	1.042	0.059	0.106	0.03
no	XXL_VLDL_FC	0.051	0.043	t-test	0.847	-0.239	0.937	0.348
no	XXL_VLDL_FC_pct	11.537	11.284	t-test	0.978	-0.032	0.055	0.013
no	XXL_VLDL_PL	0.082	0.069	t-test	0.842	-0.248	1.017	0.384
no	XXL_VLDL_PL_pct	17.037	16.536	t-test	0.971	-0.043	0.081	0.026
no	XXL_VLDL_TG_pct	54.043	42.231	t-test	0.781	-0.356	1.188	0.407

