Lactobacillus is a type of lactic acid bacterium commonly found in the human gastrointestinal tract and in fermented dairy products such as cheese, yogurt, and kefir [14]. The isolation of specific probiotic strains for targeted application is a strategy for improving the efficacy of probiotic supplements. Some species of *Lactobacillus*, such as *L. gasseri* and *L. rhamnosus*, have been evaluated for inducing weight loss [15]. *Lactobacillus delbrueckii* ssp. *bulgaricus* (*L. bulgaricus*) is one of the most common lactobacilli starters used in the manufacture of a large variety of fermented milk products. *L. bulgaricus* is reported to exhibit an outstanding inhibitory effect on pancreatic lipase activity in vitro and effectively managed the fat and weight accumulation and reversed the increased blood lipid, sugar, and insulin levels caused by a high-fat diet in mice [16]. Our hypothesis posits that *L. bulgaricus* can contribute to the reduction of body weight and alleviate health risk factors associated with obesity in overweight individuals. Thus, the objective of this study was to examine the effectiveness of daily *L. bulgaricus* supplementation in weight management among overweight participants. The primary goal is to evaluate its impact on lowering body weight and addressing health risk factors related to obesity, including blood lipid levels, sugar regulation, and insulin levels.

IRB/REC No. :	CMUH110-REC2-070
Page No. :	4/28

Methods and Design

Participants:

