Enrolled participants were randomly divided into probiotics group or placebo group. Seventeen and 19 participants were respectively assigned to the placebo group and the probiotics group. The probiotics we used were in the form of 100mg L. bulgaricus powder packets, each containing 1×10^8 CFU of probiotics (TCI CO., Taipei, Taiwan). Initially (day 1), participants underwent measurements for weight, body fat, and BMI, and fasting blood

[figure not shown]
IRB/REC No. :	CMUH110-REC2-070
Page No. :	5/28

samples were collected. Subsequently, each participant received one package of either probiotic or a placebo sample, along with drinking water on the same day. From that point onward, participants self-administered one package of the sample daily for 12 weeks and the participants' sample consumption and physical conditions were tracked by the research assistants weekly. Throughout the study duration, participants maintained their regular diet and lifestyle. At the endpoint (day 84), weight, body fat, and BMI were measured, and fasting blood samples were collected again. Weight and body fat were measured with Karada Scan 216 (OMRON, Kyoto, Japan). Alanine aminotransferase (ALT), aspartate aminotransferase (AST), blood urea nitrogen (BUN), creatinine (CRE), CHOL, HDL-C, LDL-C, TG, hemoglobin A1c (HbA1c), and Glucose-Ante Cibum (Glu-AC) levels were analyzed and reported by Laboratory Medicine in Chinese Medical University Hospital (Taichung, Taiwan). Data were expressed as the mean \pm standard error of the mean (SEM). Statistical significance between groups were done by student paired t-test or Mann-Whitney test. P-values lower than 0.05 were considered statistically significant.

Data Analysis:

The statistical analysis was conducted using GraphPad's unpaired independent samples t-test, with significance set at $*P < 0.05$.

Flow Diagram of the study:

Group	Placebo		Probiotics	
	Mean	SD	Mean	SD
Age, years	41.38	12.71	41.56	10.92
Gender, male/female	7/6		12/6	
Weight, kg	78.69	15.64	80.77	15.11
Body fat, %	32.08	6.65	30.84	5.26
BMI	29.32	5.40	28.89	3.59
ALT, U/L	26.00	15.37	32.63	18.96
AST, U/L	21.45	10.62	23.36	7.44
BUN, mg/dL	13.10	2.69	13.67	2.94
CRE, mg/dL	0.80	0.14	0.83	0.15
CHOL, mg/dL	182.18	43.04	201.60	40.97
HDL-C, mg/dL	46.82	5.82	48.50	16.26
LDL-C, mg/dL	122.82	42.15	111.01	30.40
TG, mg/dL	139.62	52.18	220.94	173.92
HbA1c, %	5.80	0.83	6.17	1.07
Glu-AC, mg/dL	93.45	16.92	109.06	34.13

Table 1: Analysis of Baseline Values of the Participants

Results

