
[figure not shown]

Figure 1: Changes in Body Composition

Placebo represents the placebo control group, and Probiotics represents the probiotics experimental group. The changes in body weight (A), body fat (B), and BMI (C) before and after consumption were calculated and expressed as a percentage of the initial values. No significant differences were observed between the two groups.

[figure not shown]

Figure 2: Changes in Blood Sugar Indices

Placebo represents the placebo control group, and Probiotics represents the probiotics experimental group. The changes in fasting blood glucose (GLU-AC) before and after sample consumption (A) and changes in glycated hemoglobin (HbA1c) expressed as a percentage of the initial values (B) were calculated. No significant differences were observed

between the two groups.

[figure not shown]

Figure 3: Changes in Blood Lipids

Placebo represents the placebo control group, and Probiotics represents the probiotics experimental group. The changes in total cholesterol (CHOL) (A), triglycerides (TG) (B), high-density lipoprotein cholesterol (HDL) (C), and low-density lipoprotein cholesterol (LDL-C) (D) before and after sample consumption were calculated. No significant differences were observed between the two groups. In the probiotics group, 65% of participants showed a decrease in TG concentration, while the placebo group had a decrease rate of 18%.

[figure not shown]

Figure 4: Changes in Liver and Kidney Function

Placebo represents the placebo control group, and Probiotics represents the probiotics experimental group. The changes in liver function indicators, aspartate aminotransferase (AST) (A) and alanine aminotransferase (ALT) (B), as well as kidney function indicators, creatinine (CRE) (C) and blood urea nitrogen (BUN) (D), before and after sample consumption were calculated. No significant differences were observed between the two groups.

IRB/REC No. :	CMUH110-REC2-070
Page No. :	10/28

Table 2: Comparative Analysis of Blood Biochemical Indices Before and After the Experiment and Changes Before and After

Variables		Probiotics	Placebo	P-value ^b
		Mean \pm SEM	Mean \pm SEM	
ALT (U/L)	Pre	32.00 \pm 4.495	31.00 \pm 6.454	0.9897
	Post	28.12 \pm 4.853	37.69 \pm 7.946	0.7713
	Change	-3.882 \pm 3.461	6.692 \pm 6.747	0.5075
	P-value ^a	0.2462	0.3799	
AST (U/L)	Pre	24.31 \pm 1.886	22.38 \pm 3.054	0.3909
	Post	22.44 \pm 2.238	25.85 \pm 4.366	0.9053
	Change	-1.875 \pm 1.530	3.462 \pm 2.043	0.34

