Placebo represents the placebo control group, and Probiotics represents the probiotics experimental group. Individual comparisons of changes in lipids carried by serum lipoproteins before and after sample consumption are depicted. The size of the points in the scatter plot ($-\log_{10}$ p values) and the color (log2 fold change denoted as log2FC, with red indicating positive correlation changes and blue indicating negative correlation changes) are used to distinguish between inter-group differences and trends. Serum very low-density lipoprotein (VLDL), low-density lipoprotein (LDL), and high-density lipoprotein (HDL) have the ability to carry cholesterol (Chol), lipids, cholesterol esters (CE), and triglycerides (TG) individually. The experimental data indicate that probiotics upregulate the content of

IRB/REC No. :	CMUH110-REC2-070
Page No. :	13/28

lipids carried by HDL (Chol:Lipid and CE:Lipid). Simultaneously, there is a significant decrease in the total amount of lipids carried by VLDL (L-VLDL, XL-VLDL, XXL-VLDL). Additionally, there is a significant decrease in triglycerides (TG) carried by both VLDL and HDL.

IRB/REC No. :	CMUH110-REC2-070
Page No. :	14/28

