Appendix

Figure 5: Extracted Meaningful Components from Metabolomic Analysis Results, Other Results Provided in the Appendix °

Table 3: List of Name Abbreviations and Units

Excel column name	Biomarker name	Unit
Total-C	Total cholesterol	mmol/l
non-HDL-C	Total cholesterol minus HDL-C	mmol/l
Remnant-C	Remnant cholesterol (non-HDL, non-LDL -cholesterol)	mmol/l
VLDL-C	VLDL cholesterol	mmol/l
Clinical LDL-C	Clinical LDL cholesterol	mmol/l
LDL-C	LDL cholesterol	mmol/l
HDL-C	HDL cholesterol	mmol/l
Total-TG	Total triglycerides	mmol/l
VLDL-TG	Triglycerides in VLDL	mmol/l
LDL-TG	Triglycerides in LDL	mmol/l
HDL-TG	Triglycerides in HDL	mmol/l
Total-PL	Total phospholipids in lipoprotein particles	mmol/l
VLDL-PL	Phospholipids in VLDL	mmol/l
LDL-PL	Phospholipids in LDL	mmol/l
HDL-PL	Phospholipids in HDL	mmol/l
Total-CE	Total esterified cholesterol	mmol/l
VLDL-CE	Cholesteryl esters in VLDL	mmol/l
LDL-CE	Cholesteryl esters in LDL	mmol/l
HDL-CE	Cholesteryl esters in HDL	mmol/l
Total-FC	Total free cholesterol	mmol/l
VLDL-FC	Free cholesterol in VLDL	mmol/l
LDL-FC	Free cholesterol in LDL	mmol/l
HDL-FC	Free cholesterol in HDL	mmol/l
Total-L	Total lipids in lipoprotein particles	mmol/l
VLDL-L	Total lipids in VLDL	mmol/l
LDL-L	Total lipids in LDL	mmol/l
HDL-L	Total lipids in HDL	mmol/l
Total-P	Total concentration of lipoprotein particles	mmol/l
VLDL-P	Concentration of VLDL particles	mmol/l
LDL-P	Concentration of LDL particles	mmol/l
HDL-P	Concentration of HDL particles	mmol/l
VLDL size	Average diameter for VLDL particles	nm
LDL size	Average diameter for LDL particles	nm
HDL size	Average diameter for HDL particles	nm
Phosphoglyc	Phosphoglycerides	mmol/l

IRB/REC No. :	CMUH110-REC2-070
Page No. :	15/28

TG/PG	Ratio of triglycerides to phosphoglycerides	ratio
Cholines	Total cholines	mmol/l
Phosphatidylc	Phosphatidylcholines	mmol/l
Sphingomyelins	Sphingomyelins	mmol/l
ApoB	Apolipoprotein B	g/l
ApoA1	Apolipoprotein A1	g/l
ApoB/ApoA1	Ratio of apolipoprotein B to apolipoprotein A1	ratio
Total-FA	Total fatty acids	mmol/l
Unsaturation	Degree of unsaturation	degree
Omega-3	Omega-3 fatty acids	mmol/l
Omega-6	Omega-6 fatty acids	mmol/l
PUFA	Polyunsaturated fatty acids	mmol/l
MUFA	Monounsaturated fatty acids	mmol/l
SFA	Saturated fatty acids	mmol/l
LA	Linoleic acid	mmol/l
DHA	Docosahexaenoic acid	mmol/l
Omega-3 %	Ratio of omega-3 fatty acids to total fatty acids	%
Omega-6 %	Ratio of omega-6 fatty acids to total fatty acids	%

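### Every lipid claim of significance or effect for the probiotic rests on components selected from a 250-feature panel that the Methods do not name, tested within one arm, with no feature passing adjustment

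*Combined protocol and SAP*

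**What the plan says.** The objective, at the end of Background, refers to lipids only in general terms: "addressing health risk factors related to obesity, including blood lipid levels, sugar regulation, and insulin levels". Methods and Design (Study Design and Intervention) lists three body measures and ten hospital blood tests: "Alanine aminotransferase (ALT), aspartate aminotransferase (AST), blood urea nitrogen (BUN), creatinine (CRE), CHOL, HDL-C, LDL-C, TG, hemoglobin A1c (HbA1c), and Glucose-Ante Cibum (Glu-AC) levels". The lipids among them are CHOL, HDL-C, LDL-C and TG. Data Analysis gives one method, "The statistical analysis was conducted using GraphPad's unpaired independent samples t-test", and the threshold in the Methods is "P-values lower than 0.05 were considered statistically significant". No metabolomic or lipoprotein-subclass assay is named in these sections, and there is no multiplicity rule.

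In Results, the Figure 3 legend reports the four hospital lipids: "No significant differences were observed between the two groups. In the probiotics group, 65% of participants showed a decrease in TG concentration", against 18% on placebo. Table 2 gives their between-group p-values.

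The Figure 5 legend then turns to the panel. It opens its conclusion with "The experimental data indicate that probiotics upregulate the content of" lipids in HDL, and goes on to claim significant falls in total lipids of L-, XL- and XXL-VLDL and in triglyceride carried by VLDL and by HDL. The note that opens the Appendix describes the figure as "Extracted Meaningful Components from Metabolomic Analysis Results, Other Results Provided in the Appendix". Table 3 lists the panel. Tables 4 and 5 print before-after results for the placebo and the probiotics group separately.

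**The concern.** The lipids that the Methods name show no significant difference between the arms. The causal and significance wording appears only when the text moves to an assay that the plan does not mention, and to components chosen from its results. A reader could leave with the view that the product changes HDL and VLDL lipids. That view would rest on selected within-arm changes, not on a randomised comparison.

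**Working it through.** The argument rests on the legend text and Tables 2 to 5, not on the plotted points of Figure 5.

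**1. Size of the panel.** Table 3 lists 82 general features, then 7 quantities and 5 ratios for each of 14 lipoprotein subclasses: 82 + 14 × 7 + 14 × 5 = 250.

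**2. Reproducing the printed adjusted p-values.** With p = 10^(−x), where x is the printed −log10 value, a Benjamini-Hochberg adjustment with m = 250 gives, for Table 5:

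- M_HDL_C_pct (rank 1): p = 10^(−3.121) = 0.00076; × 250/1 = 0.189
- M_HDL_CE_pct (rank 2): p = 10^(−2.902) = 0.00125; × 250/2 = 0.157

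The step-up rule gives both features 0.157, and −log10(0.157) = 0.805, as printed. The third and fourth features come out at 0.645 and 0.533, also as printed. For the placebo group (Table 4) the smallest adjusted value computes to 0.526 on the −log10 scale, against 0.527 printed (adjusted p = 0.297).

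**3. Features that pass.**

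| | Flagged, unadjusted p < 0.05 | Smallest adjusted p | Pass at adjusted 0.05 |
|---|---|---|---|
| Probiotics (Table 5) | 30 of 250 | 0.157 | 0 |
| Placebo (Table 4) | 8 of 250 | 0.297 | 0 |

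With no true change, 250 × 0.05 = 12.5 flags per arm are expected. These features are strongly correlated, so the actual count can vary widely around that figure.

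**4. Legend claims against Table 5 (unadjusted p).**

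Total lipids by VLDL subclass:

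| Subclass | −log10 p | p | Flag | Named in legend |
|---|---|---|---|---|
| XXL | 1.494 | 0.032 | yes | yes |
| XL | 1.334 | 0.046 | yes | yes |
| L | 1.334 | 0.046 | yes | yes |
| M | 0.434 | 0.37 | no | no |
| S | 0.123 | 0.75 | no | no |
| XS | 0.045 | 0.90 | no | no |

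The named subclasses are exactly the flagged ones. VLDL_L, the total over all VLDL, has p = 10^(−0.708) = 0.20.

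- Triglyceride in VLDL: VLDL_TG is flagged (p = 10^(−1.355) = 0.044), but its adjusted p is 10^(−0.407) = 0.39.
- Triglyceride in HDL: HDL_TG has p = 10^(−0.361) = 0.44. The four HDL subclass amounts have p from 0.37 to 0.58. Only two ratios, M_HDL_TG_pct and S_HDL_TG_pct, are flagged.
- HDL cholesterol: the claim rests on ratios in M-, S- and XL-HDL. L_HDL_C_pct (p = 0.34) is not flagged, nor are the amounts HDL_C (0.71), HDL_CE (0.79) and HDL_L (0.52).
- Total_TG has p = 0.097 and is not flagged.

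**5. The comparison made.** Table 5 is before against after within the probiotics group, and Table 4 the same within placebo. No between-group result for any panel feature is printed.

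**6. The lipids named in the Methods.** Table 2 prints these between-group p-values for change: CHOL 0.5075, HDL-C 0.9872, LDL-C 0.0946, TG 0.0555. I take them as printed, with one caution. For LDL-C the difference is 6.012 − (−12.04) = 18.05, with standard error √(4.366² + 6.323²) = 7.68, so t = 2.35. With assumed group sizes of 16–17 and 12–13, an unpaired t-test gives p of about 0.02 to 0.03, in a direction that favours placebo. The test behind the printed value therefore needs confirming.

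**7. Direction.** FC equals the column labelled before divided by the column labelled after: L_VLDL_L 0.48/0.563 = 0.853. By the printed labels L-VLDL lipids rose, while the legend says they fell. The labels and the legend must be reconciled.

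**The case against.** The strongest case on the other side has five parts.

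**Nothing was hidden or dropped.** A reader might infer outcome switching, or that the panel replaces the named lipids. The documents do not support that. All four hospital lipids are reported with between-group p-values, the Figure 3 legend states the null result plainly, and Tables 4 and 5 print every feature for both arms with adjusted p-values. The panel is an addition; what it carries is the positive lipid message.

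**The panel is not the only source of a favourable lipid statement.** The Figure 3 legend gives 65% against 18% with a TG decrease, from a lipid named in the Methods. This stands, but the statement is descriptive: no test is reported and the Methods define no responder outcome. Counts assumed from the percentages (11/17 against 2/11, 2/13 or 3/13) give Fisher p-values of 0.010 to 0.033. However, 18% matches no count out of 13, the placebo size implied by Table 1 and Table 2: (52.18/14.47)² = 13.0.

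**Unplanned is inferred from silence.** The file is version 02 with the status of a final report. Its Methods are not a complete record of intent, since the objective names insulin and the Methods list no insulin assay. An earlier version may have planned the panel. This stands, and the recommendation allows for it.

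**Result-driven display is not proved by one phrase.** The figure could show whole lipoprotein classes. That is possible for the plotted points. It does not explain why the legend's text names only the flagged VLDL subclasses.

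**Thirty flags against eight looks like a signal.** Comparing counts of within-arm significance is not a test between arms, and no feature passes adjustment in either arm.

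A reader might also count 250 panel features against 13 listed measurements and treat the ratio as a measure of bias. It is not one: the features are correlated, several duplicate listed analytes, and many are not lipids.

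**Conclusion.** The concern holds in this form. The claims that the probiotic raises HDL lipid content and significantly lowers VLDL lipids and VLDL and HDL triglycerides are not supported as stated. They come from a panel absent from the objective and Methods, and from a before-after comparison in one arm. For VLDL total lipids the named subclasses coincide with the unadjusted flags, 3 of 6. At the table's own adjusted p-values, 0 of 250 features pass. The HDL triglyceride claim fails even unadjusted when read as an amount (p about 0.44).

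This rests on the printed p-values being correct and on the document being the full public record of the plan. If an earlier dated version planned the panel, the post hoc label would change, but the within-arm comparison and the adjusted p-values would not.

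**What to change.** 1. Base the lipid conclusion on the between-group results for CHOL, TG, HDL-C and LDL-C, after confirming which test produced the Table 2 p-values. Describe the 65% against 18% statement as descriptive.
2. Label Figure 5 and its text post hoc and exploratory. If an earlier dated version planned the panel, cite it instead.
3. Replace the causal and significance wording in the legend with hypothesis-generating wording that reports the adjusted p-values and says that the comparison is within group. Separate ratios from amounts for HDL triglyceride.
4. State the rule by which the Figure 5 components were chosen.
5. Reconcile the before and after labels, the FC definition and the direction given in the legend.

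Items 2 to 4 mean rewording one legend and one heading and adding a sentence on selection. Items 1 and 5 need a check against the analysis files. The downside for the sponsor is a less favourable lipid message.

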S-VLDL-PL %	Phospholipids to total lipids ratio in small VLDL	%
S-VLDL-C %	Cholesterol to total lipids ratio in small VLDL	%
S-VLDL-CE %	Cholesteryl esters to total lipids ratio in small VLDL	%
S-VLDL-FC %	Free cholesterol to total lipids ratio in small VLDL	%
S-VLDL-TG %	Triglycerides to total lipids ratio in small VLDL	%
XS-VLDL-PL %	Phospholipids to total lipids ratio in very small VLDL	%
XS-VLDL-C %	Cholesterol to total lipids ratio in very small VLDL	%
XS-VLDL-CE %	Cholesteryl esters to total lipids ratio in very small VLDL	%
XS-VLDL-FC %	Free cholesterol to total lipids ratio in very small VLDL	%
XS-VLDL-TG %	Triglycerides to total lipids ratio in very small VLDL	%
IDL-PL %	Phospholipids to total lipids ratio in IDL	%
IDL-C %	Cholesterol to total lipids ratio in IDL	%

IRB/REC No. :	CMUH110-REC2-070
Page No. :	19/28

IDL-CE %	Cholesteryl esters to total lipids ratio in IDL	%
IDL-FC %	Free cholesterol to total lipids ratio in IDL	%
IDL-TG %	Triglycerides to total lipids ratio in IDL	%
L-LDL-PL %	Phospholipids to total lipids ratio in large LDL	%
L-LDL-C %	Cholesterol to total lipids ratio in large LDL	%
L-LDL-CE %	Cholesteryl esters to total lipids ratio in large LDL	%
L-LDL-FC %	Free cholesterol to total lipids ratio in large LDL	%
L-LDL-TG %	Triglycerides to total lipids ratio in large LDL	%
M-LDL-PL %	Phospholipids to total lipids ratio in medium LDL	%
M-LDL-C %	Cholesterol to total lipids ratio in medium LDL	%
M-LDL-CE %	Cholesteryl esters to total lipids ratio in medium LDL	%
M-LDL-FC %	Free cholesterol to total lipids ratio in medium LDL	%
M-LDL-TG %	Triglycerides to total lipids ratio in medium LDL	%
S-LDL-PL %	Phospholipids to total lipids ratio in small LDL	%
S-LDL-C %	Cholesterol to total lipids ratio in small LDL	%
S-LDL-CE %	Cholesteryl esters to total lipids ratio in small LDL	%
S-LDL-FC %	Free cholesterol to total lipids ratio in small LDL	%
S-LDL-TG %	Triglycerides to total lipids ratio in small LDL	%
XL-HDL-PL %	Phospholipids to total lipids ratio in very large HDL	%
XL-HDL-C %	Cholesterol to total lipids ratio in very large HDL	%
XL-HDL-CE %	Cholesteryl esters to total lipids ratio in very large HDL	%
XL-HDL-FC %	Free cholesterol to total lipids ratio in very large HDL	%
XL-HDL-TG %	Triglycerides to total lipids ratio in very large HDL	%
L-HDL-PL %	Phospholipids to total lipids ratio in large HDL	%
L-HDL-C %	Cholesterol to total lipids ratio in large HDL	%
L-HDL-CE %	Cholesteryl esters to total lipids ratio in large HDL	%

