no	XL_HDL_CE	0.042	0.04	t-test	0.956	-0.066	0.391	0.06
no	XL_HDL_CE_pct	40.214	33.187	t-test	0.825	-0.277	0.605	0.06
no	XL_HDL_C_pct	58.772	46.379	t-test	0.789	-0.342	0.52	0.06
no	XL_HDL_FC	0.016	0.016	t-test	1.001	0.002	0.009	0.002
no	XL_HDL_FC_pct	18.557	13.192	t-test	0.711	-0.492	0.429	0.06
no	XL_HDL_L	0.105	0.106	t-test	1.008	0.011	0.052	0.005
no	XL_HDL_P	0	0	t-test	0.985	-0.022	0.141	0.01
no	XL_HDL_PL	0.041	0.043	t-test	1.053	0.074	0.239	0.06
no	XL_HDL_PL_pct	33.404	33.946	t-test	1.016	0.023	0.143	0.01
no	XL_HDL_TG	0.006	0.006	t-test	1.095	0.131	0.319	0.06
no	XL_HDL_TG_pct	7.824	5.389	t-test	0.689	-0.538	0.301	0.06
no	XL_VLDL_C	0.054	0.055	t-test	1.019	0.027	0.072	0.005
no	XL_VLDL_CE	0.033	0.033	t-test	1.024	0.034	0.119	0.005
no	XL_VLDL_CE_pct	18.462	17.45	t-test	0.945	-0.081	0.188	0.031
no	XL_VLDL_C_pct	28.74	27.987	t-test	0.974	-0.038	0.109	0.005
no	XL_VLDL_FC	0.022	0.022	t-test	1.012	0.017	0.03	0.002
no	XL_VLDL_FC_pct	10.278	10.537	t-test	1.025	0.036	0.153	0.013
no	XL_VLDL_L	0.203	0.207	t-test	1.024	0.034	0.062	0.005
no	XL_VLDL_P	0	0	t-test	1.03	0.043	0.083	0.005
no	XL_VLDL_PL	0.036	0.036	t-test	1.014	0.019	0.032	0.002
no	XL_VLDL_PL_pct	16.268	17.052	t-test	1.048	0.068	0.342	0.06
no	XL_VLDL_TG	0.113	0.116	t-test	1.03	0.042	0.065	0.005
no	XL_VLDL_TG_pct	54.992	54.962	t-test	0.999	-0.001	0.003	0.002
no	XS_VLDL_C	0.142	0.144	t-test	1.018	0.026	0.137	0.01
no	XS_VLDL_CE	0.096	0.095	t-test	0.992	-0.011	0.053	0.005
no	XS_VLDL_CE_pct	32.455	30.476	t-test	0.939	-0.091	1	0.06
no	XS_VLDL_C_pct	47.868	46.003	t-test	0.961	-0.057	0.812	0.06
no	XS_VLDL_FC	0.046	0.049	t-test	1.073	0.102	0.693	0.06
no	XS_VLDL_FC_pct	15.413	15.527	t-test	1.007	0.011	0.23	0.06
no	XS_VLDL_L	0.293	0.313	t-test	1.068	0.095	0.627	0.06
no	XS_VLDL_P	0	0	t-test	1.055	0.078	0.522	0.06

IRB/REC No. :	CMUH110-REC2-070
Page No. :	24/28

no	XS_VLDL_PL	0.084	0.093	t-test	1.104	0.143	0.918	0.06
no	XS_VLDL_PL_pct	28.565	29.508	t-test	1.033	0.047	1.022	0.06
no	XS_VLDL_TG	0.067	0.076	t-test	1.127	0.173	0.818	0.06
no	XS_VLDL_TG_pct	23.567	24.49	t-test	1.039	0.055	0.322	0.06
no	XXL_VLDL_C	0.046	0.049	t-test	1.084	0.116	0.161	0.018
no	XXL_VLDL_CE	0.028	0.032	t-test	1.137	0.185	0.331	0.06
no	XXL_VLDL_CE_pct	23.207	26.711	t-test	1.151	0.203	0.268	0.06
no	XXL_VLDL_C_pct	36.128	39.55	t-test	1.095	0.131	0.171	0.026
no	XXL_VLDL_FC	0.018	0.018	t-test	1.001	0.001	0.001	0.001
no	XXL_VLDL_FC_pct	12.921	12.839	t-test	0.994	-0.009	0.011	0.002
no	XXL_VLDL_L	0.156	0.149	t-test	0.957	-0.064	0.054	0.005

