no	XXL_VLDL_P	0	0	t-test	0.992	-0.012	0.01	0.002
no	XXL_VLDL_PL	0.026	0.026	t-test	0.986	-0.021	0.017	0.002
no	XXL_VLDL_PL_pct	14.889	16.636	t-test	1.117	0.16	0.527	0.06
no	XXL_VLDL_TG	0.084	0.074	t-test	0.879	-0.187	0.136	0.01
no	XXL_VLDL_TG_pct	34.697	43.814	t-test	1.263	0.337	0.413	0.06

IRB/REC No. :	CMUH110-REC2-070
Page No. :	25/28

Table 5: Comparative Analysis of Metabolomic Pre-test and Post-test Results for Probiotics Group Blood Samples

Differential expression analysis								
Significance(p-value)	Feature	Mean(after)	Mean(before)	Method	FC	Log2(FC)	-Log10(p-value)	-Log10(padj)
yes	Acetate	0.017	0.019	t-test	1.156	0.209	1.329	0.407
yes	Gly	0.263	0.295	t-test	1.123	0.167	1.447	0.407
yes	HDL_size	9.573	9.508	t-test	0.993	-0.01	1.433	0.407
yes	Lactate	4.175	5.984	t-test	1.433	0.519	1.441	0.407
yes	L_VLDL_CE_pct	14.036	15.354	t-test	1.094	0.129	1.363	0.407
yes	L_VLDL_C_pct	28.119	29.999	t-test	1.067	0.093	1.505	0.407
yes	L_VLDL_FC_pct	14.083	14.645	t-test	1.04	0.056	1.643	0.421
yes	L_VLDL_L	0.563	0.48	t-test	0.853	-0.229	1.334	0.407
yes	L_VLDL_TG	0.288	0.233	t-test	0.81	-0.304	2.037	0.533
yes	L_VLDL_TG_pct	51.128	49.056	t-test	0.959	-0.06	1.429	0.407
yes	M_HDL_CE_pct	37.7	39.269	t-test	1.042	0.059	2.902	0.805
yes	M_HDL_C_pct	46.11	47.515	t-test	1.03	0.043	3.121	0.805
yes	M_HDL_PL_pct	47.018	46.34	t-test	0.986	-0.021	1.977	0.533
yes	M_HDL_TG_pct	6.873	6.145	t-test	0.894	-0.161	1.715	0.463
yes	M_VLDL_PL_pct	21.414	22.043	t-test	1.029	0.042	1.319	0.407
yes	S_HDL_CE_pct	27.533	28.901	t-test	1.05	0.07	1.987	0.533
yes	S_HDL_C_pct	37.973	39.337	t-test	1.036	0.051	2.162	0.533
yes	S_HDL_PL_pct	55.964	55.036	t-test	0.983	-0.024	1.839	0.52
yes	S_HDL_TG_pct	6.063	5.628	t-test	0.928	-0.107	1.571	0.407
yes	S_LDL_C_pct	62.862	63.718	t-test	1.014	0.019	2.566	0.645
yes	TG_by_PG	0.778	0.696	t-test	0.895	-0.161	1.792	0.508
yes	VLDL_size	39.666	39.173	t-test	0.988	-0.018	2.006	0.533
yes	VLDL_TG	1.623	1.384	t-test	0.853	-0.229	1.355	0.407
yes	XL_HDL_CE_pct	36.249	38.447	t-test	1.061	0.085	1.922	0.524
yes	XL_HDL_C_pct	52.182	56.422	t-test	1.081	0.113	1.345	0.407
yes	XL_VLDL_L	0.381	0.323	t-test	0.847	-0.239	1.334	0.407
yes	XL_VLDL_TG	0.221	0.181	t-test	0.818	-0.291	1.843	0.52
yes	XXL_VLDL_L	0.467	0.375	t-test	0.804	-0.315	1.494	0.407
yes	XXL_VLDL_P	0	0	t-test	0.817	-0.292	1.395	0.407
yes	XXL_VLDL_TG	0.267	0.202	t-test	0.756	-0.403	2.073	0.533
no	Acetoacetate	0.026	0.017	t-test	0.651	-0.619	0.697	0.243
no	Acetone	0.016	0.02	t-test	1.238	0.308	0.6	0.219

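### Three sets of lipoprotein composition means in Tables 4 and 5 total 85.714% or 88.889% instead of 100%, so those rows are wrong and must be recomputed

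*Combined protocol and SAP*

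**What the plan says.** Appendix, Table 3 defines the percentage features as ratios to the particle's total lipids, for example "Cholesterol to total lipids ratio in very large HDL". Tables 4 (placebo) and 5 (probiotics) print Mean(after), Mean(before), a fold change and P values for each feature. They give no number of participants, no detection limit and no rule for a particle that is absent or not measured.

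The placebo XL_HDL rows read "XL_HDL_C_pct 58.772 46.379", "XL_HDL_CE_pct 40.214 33.187", "XL_HDL_PL_pct 33.404 33.946" and "XL_HDL_TG_pct 7.824 5.389". The XXL_VLDL triglyceride rows read "XXL_VLDL_TG_pct 34.697 43.814" for placebo and "XXL_VLDL_TG_pct 54.043 42.231" for probiotics.

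The Figure 5 legend in Results says that the plot separates differences between groups, and that probiotics raise "lipids carried by HDL (Chol:Lipid and CE:Lipid").

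**The concern.** Cholesterol, phospholipids and triglycerides make up the whole of each particle's lipid in these tables. If every participant's shares total 100%, so do the mean shares. A total of 86% or 89% means that some participants contributed something that is not a composition.

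A concentration of zero can be a valid result. A composition of 0% for every component cannot: with no lipid present the share is 0/0. Averaging it in pulls every component mean down at one visit only, which distorts the fold change and its P value. One affected set, placebo XL_HDL, is the comparator for two probiotics rows flagged significant (XL_HDL_C_pct and XL_HDL_CE_pct), so any reading across arms for that subclass is at risk.

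**Working it through.** **1. Reproduce the printed fold change.** Table 4, placebo XL_HDL_C_pct: before/after = 46.379/58.772 = 0.789, log2 = −0.342. Both match the table. The printed fold change is therefore before divided by after.

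**2. Closure check.** I summed C% + PL% + TG% for 14 subclasses × 2 visits × 2 arms = 56 sets. In 53 the total is 100 within 0.002. The exceptions, by printed column label, are:

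| Set | C% + PL% + TG% | Total | Same subclass and arm, other visit |
|---|---|---|---|
| Placebo XL_HDL before | 46.379 + 33.946 + 5.389 | 85.714 | 100.000 |
| Placebo XXL_VLDL after | 36.128 + 14.889 + 34.697 | 85.714 | 100.000 |
| Probiotics XXL_VLDL before | 30.122 + 16.536 + 42.231 | 88.889 | 99.999 |

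Within the first set, cholesteryl ester plus free cholesterol still equals cholesterol (33.187 + 13.192 = 46.379). A misread digit is therefore not the cause.

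**3. What the totals suggest.** 6/7 = 85.714% and 8/9 = 88.889%. For group sizes from 2 to 19, only 6/7 or 12/14 gives the first and only 8/9 or 16/18 the second. All-zero compositions in 1 of 7 (or 2 of 14) placebo participants and 1 of 9 (or 2 of 18) probiotics participants would produce exactly this. Seventeen and 19 were randomised; by the sex counts, Table 1 shows 13 and 18.

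**4. Illustration by rescaling** (mean over non-zero compositions, ×7/6 or ×9/8):

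- Placebo XL_HDL_C_pct: 46.379 × 7/6 = 54.109; 54.109/58.772 = 0.921 (printed 0.789).
- Placebo XL_HDL_CE_pct: 33.187 × 7/6 = 38.718; 38.718/40.214 = 0.963 (printed 0.825).
- Placebo XXL_VLDL_C_pct: 36.128 × 7/6 = 42.149; 39.550/42.149 = 0.938 (printed 1.095).
- Probiotics XXL_VLDL_TG_pct: 42.231 × 9/8 = 47.510; 47.510/54.043 = 0.879 (printed 0.781).

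This compares unequal sets of participants at the two visits, so it is not the proposed analysis.

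**5. Complete pairs.** Let x be the dropped placebo participant's XL_HDL_C_pct at the other visit (the mean of two such values if n = 14). Fold change = 7 × 46.379/(7 × 58.772 − x) = 324.653/(411.404 − x).

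| x | Fold change |
|---|---|
| 0 | 0.789 |
| 30 | 0.851 |
| 60 | 0.924 |
| 100 | 1.043 |

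Any positive x gives more than 0.789. For placebo XXL_VLDL_C_pct the fold change is (7 × 39.550 − x)/(7 × 36.128) = (276.850 − x)/252.896. It falls below 1 once x exceeds 23.954, so whether the direction changes depends on a value that is not printed.

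**6. Contrast between arms, XL_HDL** (probiotics log2 fold change minus placebo). The probiotics values, 0.113 (C%) and 0.085 (CE%), are sound. From unrounded ratios, the C% contrast is 0.454 as printed and 0.232 rescaled; the CE% contrast is 0.362 and 0.140. With complete pairs the C% contrast is 0.113 + 0.232 = 0.345 at x = 30 and 0.113 − 0.060 = 0.053 at x = 100.

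**7. Reach.** The probiotics M_HDL, S_HDL and XL_HDL sets all total 100 within 0.002. Every row in the three deficient sets is flagged no. Examples are placebo XL_HDL_C_pct, P = 10^−0.52 ≈ 0.30; CE_pct, P = 10^−0.605 ≈ 0.25; and probiotics XXL_VLDL_TG_pct, P = 10^−1.188 ≈ 0.065.

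**The case against.** The strongest reply is that nothing the report concludes is shown to change. The HDL statement under Figure 5 matches flagged probiotics rows for M_HDL, S_HDL and XL_HDL, all of which close. The VLDL statements concern lipid and triglyceride amounts, not the affected percentages. The smallest adjusted P in Table 5 is 10^−0.805 ≈ 0.16, so no feature survives adjustment in any case. All of this stands, and it limits the reach of the point. It does not make a composition of 86% valid.

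The cause is also inferred. Missing values exported as 0 would give the same totals as undetectable particles. That stands too, but the remedy is the same for both.

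Three stronger readings are tempting and unsupported:

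- A reader might infer that the Figure 5 HDL finding rests on this error. The flagged rows are intact, and the figure is not shown, so whether it plots the placebo XL_HDL values cannot be checked.
- A reader might infer that a between-arm test would show a spurious probiotic benefit. A rough reconstruction from the printed P values (assuming paired tests, 7 placebo and 9 probiotics) gives, for C%, a difference of 4.240 + 12.393 = 16.633 with standard error √(10.98² + 1.79²) ≈ 11.12 and a Welch P of about 0.18. The false zero shifts the mean but also inflates the variance. A pooled test gives about 0.11, or about 0.03 if the probiotics n is 18. So the error could bias such a test; that it would create a benefit is not shown.
- A reader might speak of a placebo fall in XL_HDL cholesterol share. As labelled, the means rise from 46.379 before to 58.772 after. A fall follows only if the column labels are swapped, which the before/after fold change leaves open.

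**Conclusion.** The point holds as a data-handling error confined to three composition sets. Their 15 rows (five components each) have wrong means, fold changes and P values. That conclusion needs only the Table 3 definition and the printed means.

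The 0% explanation is a strong inference from exact 6/7 and 8/9 totals, not a documented fact. The same holds for the implied panel size: 7 placebo participants (14 would fit the 17 randomised but not the 13 in Table 1) and 9 or 18 on probiotics. If the inference is right, the printed placebo XL_HDL_C_pct fold change of 0.789 is too low whatever the missing value is, and the descriptive XL_HDL contrast between arms is overstated. On simple rescaling that contrast is roughly halved for C% (0.454 to 0.232) and falls by more than half for CE% (0.362 to 0.140). Exact corrected values, corrected P values and any change of direction in XXL_VLDL need participant data.

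The correction should be made before the tables are relied on. It does not overturn the within-probiotics HDL rows, and it does not touch body weight or the clinical laboratory results.

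**What to change.** Set all composition percentages for a particle to missing at any visit where its total lipids are zero, undetectable or missing, and state that rule. Analyse complete pairs. Then:

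- recompute the placebo XL_HDL and both arms' XXL_VLDL percentage rows, and the adjusted P values throughout Tables 4 and 5, since those depend on the whole set of tests;
- redraw Figure 5 if it uses any of these rows;
- print the number of pairs for each feature, and state how many participants the panel covers;
- check for each participant and visit that C + PL + TG = 100 and that CE plus free cholesterol equals C;
- confirm the Mean(after) and Mean(before) labels, because the printed fold change is before/after, and state its direction in the table heading.

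This is a rerun of existing data. The cost is the loss of one or two pairs in the affected rows, which matters for precision in a panel this small but leaves every other row's pairs intact.
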